8.13.2. ESRS II

The second subscale (ESRS II) is a 17-item questionnaire to evaluate parkinsonism and akathisia.

ESRS II consists of the following parts:

1. Tremor: scored on a 7-point item scale for 8 parts of the body. For each part of the body, frequency and amplitude are selected, assigning each one of the 8 items a score from 0=none to 6=severe. Therefore, the total score for tremor can range from 0 to 48.
2. Bradykinesia: scored on a 7-point item scale (0-6).
3. Gait and Posture: scored on a 7-point item scale (0-6).
4. Postural stability: scored on a 7-point item scale (0-6).
5. Rigidity: scored on a 7-point item scale (0-6) for 4 parts of the body. Therefore, the total score for rigidity can range from 0 to 24.
6. Expressive automatic movements: scored on a 7-point item scale (0-6).
7. Akathisia: scored on a 7-point item scale (0-6).

The total score of the 17 items can range from 0 to 102.

Total score of the 17 items and total scores change from baseline will be summarized by time point, using descriptive statistics for continuous variables.

Total score will be the sum of the 17 items. Missing items will be replaced by the average of the remaining responses within each item.

Data will be listed.

9. TOLERABILITY VARIABLES AND ANALYSIS

If more than 15% of the patients withdraw from the study before the end of the treatment period, the number of days until study discontinuation will be analyzed using Kaplan-Meier methodology with the ITT analysis set.

10. PLANNED INTERIM ANALYSIS

10.1. General

When approximately 50 patients have completed the study (including follow-up), an iDMC will perform an unblinded non-binding IA for futility based on centrally read MD- CRS part II total score.

A blinded SDR meeting will be performed prior to the IA to determine eligibility to the mITT analysis set and to classify missing data to MAR/MNAR.

Calculation of conditional power will be performed by an independent unblinded statistician, and the IA will be presented and discussed in a closed session of the iDMC. Release of randomization codes to the unblinded statistician will follow SOP GBP-RD-703.

Once the unblinded statistician and iDMC members are exposed to unblinded data, they will not be involved in decision making regarding the planned analysis of the study, or classification of missing data to MAR/MNAR.

Unblinded analysis datasets, TLGs, or simulation outputs will not be disclosed to the study team until the study is completed, database is locked and randomization codes are released for final analysis. The study team will be informed of the IA decision; communication format is described in the iDMC charter.

In order to minimize potential bias, investigators will not be informed on the parameters of the promising zone method, or on decision to increase the sample size.

The Statistical Analysis Plan and iDMC charter will be finalized before the IA is performed. Any changes in the main analysis of the primary and key secondary endpoints (eg, model specifications) will not be allowed after the IA.

10.2. Interim Analysis Procedure

The IA will include the following steps:

1. A blinded statistical data review meeting will be convened to review patient-blinded data from the patients that completed the study (including early termination). For patients that terminated early from the study, classification to MAR/MNAR will be performed. In addition, exclusion of patients from the mITT analysis set will be reviewed. The meeting will include blinded members only; iDMC members and the unblinded statistician will not take part in the discussions.
2. The sponsor will provide to the unblinded statistician the following data: disposition, demography, MD-CRS part II total scores (centrally read), the list of patients included in the mITT analysis set, and classification of missing data to MAR/MNAR. The unblinded statistician will have received the randomization codes from the randomization codes generator according to SOP GBP-RD-703.
3. The unblinded statistician will estimate the conditional power (see Section 10.4 for details) and provide the results to the iDMC.

4. The iDMC will apply futility rule (see Section 10.6) to provide recommendation to the sponsor to continue the study or stop the study for futility. This recommendation will be communicated with the sponsor while keeping the sponsor blinded, as specified in the iDMC Charter.
5. The sponsor will follow the iDMC recommendation for futility recommendations.

10.3. Data Cut for Interim Analysis

When the target number of patients (approximately 50 patients) complete the study (including follow-up; including patients that withdraw from the study) and the central reading of MD-CRS part II is available, the data will be cleaned for the IA. The IA data cut will not include data from patients that are ongoing.

Assessment of eligibility to the mITT analysis set and classification of missing data to MAR/MNAR will be performed in a blinded manner in a SDR meeting prior to the IA.

The following data will be used for the IA: disposition, demography, MD-CRS part II total scores (centrally read), the list of patients included in the mITT analysis set, and classification of missing data to MAR/MNAR.

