2.4. Sample Size and Power Considerations

The initial sample size estimation of approximately 185 patients randomized to TEV-50717 versus placebo in a 2:1 ratio (approximately 124 in the TEV-50717 group; approximately 61 in the placebo group) is the sample size required to obtain a statistically significant result in the primary analysis based on a 1-sided test for mean difference at a significance level of $\alpha=0.025$ with a power of approximately 90%, assuming a mean difference of 1.8 and a standard deviation (SD) of 3.5 in each treatment group.

Based on Protocol Amendment 05, the initial planned sample size has been reduced to approximately 65 patients randomized to TEV-50717 versus placebo in a 2:1 ratio (approximately 43 in the TEV-50717 group; approximately 22 in the placebo group).

The initial assumptions regarding the mean difference and SD are based on the change from baseline to month 6 in patients treated with trihexyphenidyl reported by [Battini et al \(2014\)](#), assuming an effect size of 55% for TEV-50717 versus placebo. The effect size of 55% was assumed based on the observed effect sizes of TEV-50717 in the pivotal studies in Huntington's disease and tardive dyskinesia. In the current study, these assumptions correspond to a mean difference of 2.0 in MD-CRS part II total score and an SD of 3.5 in each treatment group.

The rate of missing not at random (MNAR) data for the primary analysis is expected to be 10%. MNAR data will be imputed in a conservative manner as if they were obtained from patients in the placebo treatment group, regardless of the actual treatment group. As a result, the mean difference is expected to be reduced from 2.0 to 1.8 in the primary analysis. The impact of the missing data imputation on the SD is negligible.

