3. ANALYSIS SETS

3.1. Intent-to-Treat Analysis Set

The intent to treat (ITT) analysis set will include all randomized patients.

In the ITT analysis set, treatment will be assigned based on the treatment to which patients were randomized, regardless of which treatment they actually received.

For patients who discontinue the study and re-enter it (repeating the study from baseline; see Section 4.5), only the data from the repeated participation will be included in the ITT analysis set.

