7. MULTIPLE COMPARISONS AND MULTIPLICITY

The primary efficacy endpoint will be tested at the 1-sided significance level of $\alpha=0.025$.

If the primary endpoint is statistically significant (p-value ≤ 0.025), the 5 key secondary hypotheses will be tested using a hierarchical approach at the 1-sided significance level of $\alpha=0.025$, in the following order: (1) MD-CRS part I total score, (2) CaGI-I, (3) CGI-I, (4) UHDRS-TMC (centrally-read), and (5) UHDRS-TMD (centrally-read)

No multiplicity control will be applied to the sensitivity analysis or other endpoints.

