10.4. Estimation of Conditional Power

The conditional power is the probability of rejecting the null hypothesis at the final analysis, assuming the alternative hypothesis is true given the data accumulated in the interim analysis. Conditional power will be estimated given the observed data, under the following assumptions:

- effect size (true difference and standard error) is as estimated in the observed data (point estimates)
- proportion of missing data MNAR in the TEV-50717 treatment group is as in the observed data
- proportion of patients excluded from the mITT analysis set is as in the observed data

Note: the conditional power is estimated based on the observed data and does not take into account the initial assumptions that were used for estimating the initial sample size.

The primary analysis is a 1-sided test of the null hypothesis $H_0: \delta \geq 0$ versus the alternative hypothesis $H_1: \delta < 0$, where δ is the difference between TEV-50717 and placebo in change from baseline in centrally-read MD-CRS part II total score (higher score represents a more severe movement disorder, thus negative change from baseline is a good outcome).

Let n_1 be the number of patients included in the mITT analysis set in the IA, and let n_2 be the incremental number of patients between the IA and the final analysis that will be included in the mITT analysis set, such that the total number of patients in the analysis will be $n = n_1 + n_2$.

Let z_1 be the Wald statistic at the IA. The conditional power is given by (Mehta and Pocock 2011):

$$\text{CPow}(n_2|n_1, z_1) = 1 - \Phi\left(\frac{z_\alpha\sqrt{n} - z_1\sqrt{n_1}}{\sqrt{n_2}} - \frac{z_1\sqrt{n_2}}{\sqrt{n_1}}\right)$$

Calculation of the Wald statistic:

$$z_1 = \frac{-\hat{\delta}_1}{\text{se}(\hat{\delta}_1)}$$

Where, $\hat{\delta}_1$ is the estimated mean difference between TEV-50717 and placebo and $\text{se}(\hat{\delta}_1)$ is the estimated SE of the mean difference, both obtained from the primary analysis model (MMRM applying MAR/MNAR multiple imputation; see Section 6.2.3) fitted to the IA mITT data.

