10.5. Sample Size

Let n_1^* be the total sample size at the IA (ITT analysis set). Assuming that the proportion of patients that will be excluded from the mITT analysis set for the primary analysis (ie, do not have at least 1 post-baseline central reading of MD-CRS part II total score) will be as estimated in the IA, the total sample size of the study is given by

$$n^* = \frac{n_1^*}{n_1} n = n_1^* + \frac{n_1^*}{n_1} n_2$$

The sample size recommendation will be presented in terms of the total sample size n^* .

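### The interim cohort is formed by order of finishing, so it slightly over-represents withdrawals and, if the drug works, slightly lowers conditional power

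*SAP*

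**What the plan says.** Section 10.3 triggers the interim analysis when about 50 patients "complete the study (including follow-up; including patients that withdraw from the study) and the central reading of MD-CRS part II is available". It adds: "The IA data cut will not include data from patients that are ongoing". Section 10.2, step 1, likewise counts early terminations among the finished patients. Neither section ties the cohort to the order or date of randomisation.

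Under Section 2.1 a completer is finished about 17 weeks after randomisation, while a patient who stops early has a follow-up contact 2 weeks after the early termination visit.

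Section 10.4 takes the treatment difference and its standard error from this cohort and assumes that the "proportion of missing data MNAR in the TEV-50717 treatment group is as in the observed data". The share excluded from mITT is carried forward in the same way. Section 10.6 sets the futility zone at conditional power below 3% and calls the decision non-binding.

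Section 6.2.3 imputes active-arm MNAR withdrawals as if they had become placebo patients. Section 2.4 expects a 10% MNAR rate and says that this shrinks the difference from 2.0 to 1.8.

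**The concern.** A withdrawal becomes eligible for the cut as soon as its short follow-up ends; a patient who stays must wait about 17 weeks. Among the most recently randomised patients, the cut therefore admits those who stopped and omits those who are continuing. That is selection on a status related to outcome, and the first 50 to finish will on average contain a larger share of withdrawals than the full 65.

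Three things must hold together for this to lower conditional power:

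- Patients are still ongoing at the cut.
- Some active-arm withdrawals are classed MNAR and have the post-baseline central reading that keeps them in mITT.
- The drug has a real benefit, so that placebo-like imputation costs something.

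When they do, z1 is pulled toward zero and the trial is nudged toward the futility zone. The estimate is then not a neutral preview of the final analysis, and the error runs against an effective drug.

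**Working it through.** **Inputs from the SAP.** One-sided α 0.025 (Section 7); difference 1.8, SD 3.5, 2:1 allocation, 10% MNAR (2.4); total 65, as 43:22 (2.4); about 50 at the interim (10.3); conditional power formula (10.4); 3% threshold (10.6).

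**Assumed, because the SAP is silent.** Accrual of 0.4, 1 or 3 patients per week; withdrawals spread evenly over 15 weeks or over the 7-week titration only; MNAR rates of 20% and 30% as a stress test.

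**Reproducing the plan's figures.** Section 2.4 plans 124:61 patients "with a power of approximately 90%, assuming a mean difference of 1.8 and a standard deviation (SD) of 3.5 in each treatment group". SE = 3.5 × √(1/124 + 1/61) = 0.547; 1.8/0.547 = 3.29; power = Φ(3.29 − 1.96) = 90.8%. The dilution also reproduces: 2.0 × (1 − 0.10) = 1.8. At 43:22 the SE is 0.917 and power is Φ(1.96 − 1.96), about 50%.

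**The futility bound.** With n1 = 50, n2 = 15 and n = 65, conditional power equals 3% when

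(1.96√65 − z1√50)/√15 − z1√15/√50 = 1.881,

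that is, 4.080 − 2.373 z1 = 1.881, so z1 = 0.93. With SE = 3.5 × √(1/33.3 + 1/16.7) = 1.05, this is an estimated difference of about 0.97. At a true 1.8 the mean of z1 is 1.8/1.05 = 1.71, so the rule stops with probability Φ(0.93 − 1.71), about 22%. That figure comes from the threshold and the sample size, not from the cohort definition.

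**A ceiling by hand.** If every withdrawal among all 65 reached the cut of 50, the share would be at most about 0.10 × 65/50 = 13%. The difference becomes 2.0 × 0.87 = 1.74, the mean of z1 is 1.66, and the stopping probability is Φ(0.93 − 1.66) = 23.3% against 21.5%: under 2 points.

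**Simulation at 10% MNAR** (40,000 trials per row; effect 2.0 in patients who stay, 0 in active-arm MNAR withdrawals; completers finish at 17 weeks, withdrawals 2 weeks after stopping). Each pair gives the first 50 to finish, then the first 50 randomised.

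| Accrual per week | Withdrawal timing | Ongoing at cut | Active MNAR share | Mean difference | P(CPow <3%) | Rise (points) |
|---|---|---|---|---|---|---|
| 0.4 | 15 weeks | 6.6 | 10.6 v 10.0% | 1.79 v 1.80 | 22.3 v 21.9% | 0.4 |
| 0.4 | titration | 6.5 | 10.8 v 10.0% | 1.78 v 1.80 | 22.6 v 21.9% | 0.7 |
| 1 | 15 weeks | 14.0 | 11.3 v 10.0% | 1.77 v 1.80 | 22.6 v 21.7% | 0.9 |
| 1 | titration | 14.0 | 12.0 v 10.0% | 1.77 v 1.80 | 23.5 v 21.9% | 1.5 |
| 3 | 15 weeks | 15.0 | 12.3 v 10.0% | 1.75 v 1.79 | 23.5 v 22.0% | 1.6 |
| 3 | titration | 15.0 | 12.8 v 10.0% | 1.76 v 1.81 | 23.7 v 21.7% | 2.0 |

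Rises were taken before rounding. The simulation standard error of each probability is √(0.22 × 0.78/40,000), about 0.2 points. Mean conditional power falls by 0.4 to 2.4 points. A separate run at 1 to 4 patients per month gave shares of 10.5 to 11.9% and a rise of about 0.3 to 1 point.

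**Stress test.** At 20% MNAR the rise is 0.8 to 4.4 points; at 30% it is 0.9 to 6.4 points. With a true effect of zero, the two cohorts stop equally often (about 82%) within simulation error.

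The simulation applies the placebo-like imputation at the level of the mean and omits imputation variance and the repeated-measures model.

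**The case against.** The strongest reply is that the effect is trivial on the plan's own figures. One extra percentage point of MNAR among some 33 active patients is a third of a patient, and the word approximately before 50 allows more variation than that. This largely stands.

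The larger stress-test figures need 20 to 30% MNAR and fast accrual. The amendment history says the sample was cut because enrolment was slow. The first SAP and Amendment 03 are about 37 months apart; 4 patients per month over half that span would be 74, more than 65, although the SAP does not say when enrolment began.

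The simulation also takes the harshest view of a withdrawal. Section 4.3 classes loss to follow-up and COVID-19 terminations as missing at random, imputed from the patient's own arm. A patient with no post-baseline central reading leaves mITT and does not dilute z1. An early termination reading is mapped to a visit (Table 2), and Appendix 1 conditions later imputations on it. All this stands and keeps the estimate toward an upper limit.

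The non-binding status protects only in part, since Section 10.2, step 5, says the sponsor will follow the committee's recommendation.

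A reader might go further and infer that Section 10.5 miscounts. It defines n1* to "be the total sample size at the IA (ITT analysis set"), and Section 3.1 says: "The intent to treat (ITT) analysis set will include all randomized patients". On that literal reading ongoing patients would look like mITT exclusions and n2 would be too small. The SAP does not support this. Section 10.3 confines the cut to patients no longer ongoing, Section 10.5 describes exclusions as patients without a post-baseline central reading, and Section 10.4 places later mITT patients in n2.

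**Conclusion.** A minor, avoidable downward bias, conditional on a working drug, MNAR withdrawals in the active arm that stay in mITT, and patients ongoing at the cut. At the expected 10% MNAR it adds roughly 0.3 to 2 points to a stopping chance of about 22% at a true difference of 1.8; with slow accrual it lies at the small end.

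A reader might infer that conditional power is biased down whatever the truth. It is not: under no effect there is nothing to dilute. Nor is type I error affected, because the look can stop only for futility, is non-binding, and leaves the final test at 0.025.

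The size rests on assumed accrual and withdrawal timing. The futility rules also sit in the monitoring committee's charter, which is not at hand and may already define the cohort.

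**What to change.** In Section 10.3, define the interim cohort by randomisation order: the first approximately 50 patients randomised, with the cut made when each has completed the study or withdrawn and the central readings are available. State that a later-randomised patient who withdraws before the cut does not enter. In Sections 10.4 and 10.5, say that n1 and n1* are the mITT and randomised counts of that same cohort, which also closes off the literal reading of n1*. Align the charter.

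Moving the cut from end of follow-up to week 15 is not needed for this; it would not remove the selection.

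The cost is SAP and charter wording, agreed before the interim analysis. The look may come slightly later, because withdrawals among recent enrollees no longer count toward the 50. No analysis model or patient procedure changes.

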10.4. Estimation of Conditional Power

The conditional power is the probability of rejecting the null hypothesis at the final analysis, assuming the alternative hypothesis is true given the data accumulated in the interim analysis. Conditional power will be estimated given the observed data, under the following assumptions:

- effect size (true difference and standard error) is as estimated in the observed data (point estimates)
- proportion of missing data MNAR in the TEV-50717 treatment group is as in the observed data
- proportion of patients excluded from the mITT analysis set is as in the observed data

Note: the conditional power is estimated based on the observed data and does not take into account the initial assumptions that were used for estimating the initial sample size.

The primary analysis is a 1-sided test of the null hypothesis $H_0: \delta \geq 0$ versus the alternative hypothesis $H_1: \delta < 0$, where δ is the difference between TEV-50717 and placebo in change from baseline in centrally-read MD-CRS part II total score (higher score represents a more severe movement disorder, thus negative change from baseline is a good outcome).

Let n_1 be the number of patients included in the mITT analysis set in the IA, and let n_2 be the incremental number of patients between the IA and the final analysis that will be included in the mITT analysis set, such that the total number of patients in the analysis will be $n = n_1 + n_2$.

Let z_1 be the Wald statistic at the IA. The conditional power is given by (Mehta and Pocock 2011):

$$\text{CPow}(n_2|n_1, z_1) = 1 - \Phi\left(\frac{z_\alpha\sqrt{n} - z_1\sqrt{n_1}}{\sqrt{n_2}} - \frac{z_1\sqrt{n_2}}{\sqrt{n_1}}\right)$$

Calculation of the Wald statistic:

$$z_1 = \frac{-\hat{\delta}_1}{\text{se}(\hat{\delta}_1)}$$

Where, $\hat{\delta}_1$ is the estimated mean difference between TEV-50717 and placebo and $\text{se}(\hat{\delta}_1)$ is the estimated SE of the mean difference, both obtained from the primary analysis model (MMRM applying MAR/MNAR multiple imputation; see Section 6.2.3) fitted to the IA mITT data.

10.5. Sample Size

Let n_1^* be the total sample size at the IA (ITT analysis set). Assuming that the proportion of patients that will be excluded from the mITT analysis set for the primary analysis (ie, do not have at least 1 post-baseline central reading of MD-CRS part II total score) will be as estimated in the IA, the total sample size of the study is given by

$$n^* = \frac{n_1^*}{n_1} n = n_1^* + \frac{n_1^*}{n_1} n_2$$

The sample size recommendation will be presented in terms of the total sample size n^* .

10.6. Decision Rules

The following zone and corresponding actions are defined for all possible results of conditional power (CPow) is provided in Table 13.

Table 13: Decision Rules According to the Promising Zone Method for IA

Zone	Conditional Power	Decision
Futility	CPow <3%	Stop the study for futility

The futility decision is considered non-binding.

11. STATISTICAL SOFTWARE

All data listings, summaries, and statistical analyses will be generated using SAS[®] version 9.4 or later.

**12. CHANGES TO ANALYSES SPECIFIED IN THE STUDY
PROTOCOL**

No changes to the analyses specified in the protocol are planned at the time of writing this SAP amendment.

APPENDIX 1. MAR/MNAR JUMP TO REFERENCE MULTIPLE IMPUTATION METHODOLOGY

The following 3 steps will be performed to do the multiple imputation analysis:

1. Create complete data sets using imputation for each subgroup.
2. Analyze the imputed complete data sets for the combined subgroups.
3. Combine analysis results into a final result.

Step 1

In order to induce monotonicity, an imputation model will first be used to impute missing values for MD-CRS part II total score week 9, 12, and 15 change values and will use age group at baseline and baseline MD-CRS part II total score to determine the scores (500 imputations will be created).

The SAS code for the imputation is as follows:

```
proc mi data=final out=mitv1 seed=987 nimate=500;
  where arm='TEV-50717' & (missdm in ("MAR") or _9^=.); /* 1st subgroup */
  class agegrp region;
  var agegrp region base _9;
  monotone regpmm; run;

proc mi data=final out=miplb1 seed=876 nimate=500;
  where arm='PLACEBO' or (arm='TEV-50717' & missdm='MNAR' & _9=.); /* 2nd subgroup */
  class agegrp region;
  var agegrp region base _9;
  monotone regpmm; run;

data mi1; set mitv1 miplb1; run;

proc sort data=mi1; by _imputation_; run;

proc mi data=mi1 out=mitv2 seed=9876 nimate=1; by _imputation_;
  where arm='TEV-50717' & (missdm in ("MAR") or _12^=.);
  class agegrp region;
  var agegrp region base _9 _12;
  monotone regpmm; run;

proc mi data=mi1 out=miplb2 seed=8765 nimate=1; by _imputation_;
  where arm='PLACEBO' or (arm='TEV-50717' & missdm='MNAR' & _12=.);
  class agegrp region;
  var agegrp region base _9 _12;
  monotone regpmm; run;

data mi2; set mitv2 miplb2; run;

proc sort data=mi2; by _imputation_; run;

proc mi data=mi2 out=mitv3 seed=98765 nimate=1; by _imputation_;
  where arm='TEV-50717' & (missdm in ("MAR") or _15^=.);
  class agegrp region;
```

```
var agegrp region base _9 _12 _15;  
monotone regpmm; run;
```

```
proc mi data=mi2 out=miplb3 seed=87654 nimpute=1; by imputation;  
where arm='PLACEBO' or (arm='TEV-50717' & misdm='NMAR' & _15=.);  
class agegrp region;  
var agegrp region base _9 _12 _15;  
monotone regpmm; run;
```

Step 2

The resultant complete data sets will be combined for the 2 subgroups and then analyzed using mixed-model, repeated-measures with the change in MD-CRS part II total score as the dependent variable (the primary analysis). The SAS code is as follows:

```
data all; set mitv3 miplb3;  
    avisitn=9; chg=_9; output; avisitn=12; chg=_12; output; avisitn=15; chg=_15; output; run;  
proc sort data=all; by _imputation_ descending arm avisitn; run;  
proc mixed data=all order=data; by _imputation_;  
    class usubjid arm avisitn agegrp region;  
    model chg=arm avisitn arm*avisitn agegrp region base / ddfm=kr;  
    repeated avisitn / type=un subject=usubjid;  
    lsmeans arm*avisitn / diff cl;  
    ods output diffs=diff(where=(avisitn=_avisitn) lsmeans=lsm; run;
```

Step 3

The results from the imputed data analysis will be combined using PROC MIANALYZE which will provide the LS mean and standard error of the LS mean for each treatment group at each visit as well as the LS mean difference, 95% CI and resultant p-value between the TEV-50717 and placebo groups at each visit. The SAS code is as follows:

```
proc sort data=diff; by avisitn arm; run;  
proc sort data=lsm; by avisitn arm; run;  
proc mianalyze data=diff; by avisitn arm;  
    modeleffects estimate;  
    stderr stderr;  
    ods output ParameterEstimates=estdiff; run;  
proc mianalyze data=lsm; by avisitn arm;  
    modeleffects estimate;  
    stderr stderr;  
    ods output ParameterEstimates=estlsm; run;
```

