6.2.3. Primary Efficacy Analysis

The primary analysis will be a mixed-model repeated-measures (MMRM) with the change in MD-CRS part II total score as the dependent variable. The model will include fixed effects for treatment group, week (as a categorical variable with 3 levels: weeks 9, 12, and 15), and treatment group by week interaction. The baseline MD-CRS part II total score, age group at baseline (2 levels: 6 to <12 years; 12 through 18 years, inclusive), and region (US; non-US) will be included as covariates. The unstructured covariance matrix will be used in the model. In cases where the model does not converge, the Maximum-Likelihood estimation method will be used instead of the default Restricted Maximum-Likelihood. If the model still does not converge, then a simpler covariance structure with fewer parameters will be used, according to the following order: Heterogeneous Autoregressive (1), Heterogeneous Compound Symmetry, Autoregressive (1), and Compound Symmetry. The Kenward-Roger approximation will be used to estimate denominator degrees of freedom.

Missing data will be classified as MAR and MNAR, as described in Section 4.3. MNAR data will be imputed using the jump-to-reference method, and MAR data will be imputed based on the randomized treatment group. The details are described below:

1. Missing data will be imputed in 2 separate subgroups. The MAR subgroup will contain all patients randomized to a TEV-50717 treatment group without missing data at week 15 or have a MAR missing data mechanism. The MNAR subgroup will contain all patients randomized to placebo as well as patients randomized to receive TEV-50717 with missing data at week 15 with an MNAR missing data mechanism.
2. Data will be imputed for patients with missing data at week 15 using a predictive mean matching multiple imputation method. Multiple imputations will be performed within each subgroup:
 - a. Under a MNAR data assumption, patients in the MNAR subgroup will have their missing data at week 15 imputed as if they behaved like placebo treated patients after dropping out. Only placebo patients with complete data will be included in the imputation model.
 - b. All other patients will have data imputed from a model derived from their assigned treatment group (imputation under MAR assumption).

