The imputation models will include age group at baseline, region, baseline MD-CRS part II total score, and MD-CRS part II total scores at week 9 and week 12. After obtaining complete data sets for both subgroups, they will be combined and the complete data set will be used in the analysis.

3. The resulting complete, imputed datasets will each be analyzed using the analysis model described above and the resulting statistics combined using methodology presented by [Rubin \(1987\)](#) and [Little and Rubin \(2002\)](#).

The complete multiple imputation methodology, along with SAS code, is detailed in [Appendix 1](#). Difference in least squares (LS) mean of the change in MD-CRS part II total score from baseline to week 15 (TEV-50717 versus placebo) will be compared using a 1-sided test for superiority at a nominal significance level of $\alpha=0.025$.

The LS mean and SE for the treatment groups, the LS mean difference, 2-sided 95% confidence interval, and p-value for the comparison (TEV-50717 versus placebo) at week 15 will be presented.

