  ods output diffs=diff(where=(avisitn=_avisitn )) lsmeans=lsm; run;
```

Step 3

The results from the imputed data analysis will be combined using PROC MIANALYZE which will provide the LS mean and standard error of the LS mean for each treatment group at each visit as well as the LS mean difference, 95% CI and resultant p-value between the TEV-50717 and placebo groups at each visit. The SAS code is as follows:

```
proc sort data=diff; by shift avisitn arm; run;
proc sort data=lsm; by shift avisitn arm; run;

proc mianalyze data=diff; by shift avisitn arm;
  modeleffects estimate;
  stderr stderr;
  ods output ParameterEstimates=estdiff; run;

proc mianalyze data=lsm; by shift avisitn arm;
  modeleffects estimate;
  stderr stderr;

ods output ParameterEstimates=estlsm; run;
```

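### The pooling code omits EDF=, so the Kenward-Roger degrees of freedom planned in SAP section 6.2.3 do not reach the pooled p-value and confidence interval

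*SAP*

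**What the plan says.** For the primary MMRM, SAP section 6.2.3 states: "The Kenward-Roger approximation will be used to estimate denominator degrees of freedom". The PROC MIXED code in Appendix 1, Step 2 does this within each imputed data set: "model chg=arm avisitn arm*avisitn agegrp region base / ddfm=kr".

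Section 6.2.3 then has each data set "analyzed using the analysis model described above and the resulting statistics combined using methodology presented by" Rubin (1987) and Little and Rubin (2002). It names no small-sample df for the pooled result. Appendix 1 sets the number of imputations at 500.

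The pooling is Step 3 of Appendix 1: "proc mianalyze data=diff; by avisitn arm", followed only by a MODELEFFECTS and a STDERR statement. Step 3 is the source of the reported results: the LS means "as well as the LS mean difference, 95% CI and resultant p-value between the TEV-50717 and placebo groups at each visit". Appendix 2 uses the same construction for the tipping-point analysis: "proc mianalyze data=diff; by shift avisitn arm". Neither appendix has an EDF= option or any other line that carries the df forward.

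Section 7 tests the primary endpoint at one-sided 0.025 and makes the five key secondary tests conditional on it. Section 6.3.1.1 analyses those endpoints in the same way as the primary one.

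**The concern.** The choice of Kenward-Roger shows that the plan wants a small-sample reference distribution. PROC MIANALYZE knows only what it is given. Without EDF= it assumes infinite complete-data df, so the pooled df depend only on the number of imputations and the missing information. With 500 imputations the result is practically a z-test. The small-sample df are computed in Step 2 and dropped in Step 3, where the confirmatory p-value is produced.

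At stake are the nominal level of the test that gates the whole hierarchy, and the width of every pooled interval. The issue was smaller at the initial 185 patients than at the current 65 (43 and 22).

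**Working it through.** **Inputs from the SAP.** One-sided level 0.025 (section 7). m = 500 imputations (Appendix 1). About 65 patients, 43:22; initially 185, 124:61 (section 2.4). Week-15 contrast adjusted for age group, region and baseline (section 6.2.3).

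**Assumptions, not in the SAP.** Complete-data df (EDF): 65 patients minus 5 mean parameters (intercept, treatment, age group, region, baseline) = 60, with 50 as a lower value. Fraction of missing information λ: 2 to 30%, central value 10%. The 10% in section 2.4 is an expected rate of MNAR data, which is a different quantity.

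**The plan's own figure.** The SAP gives no pooled df to reproduce. Its initial sample size does reproduce. With difference 1.8 and SD 3.5, the placebo group needs 1.5 × (1.960 + 1.282)² × 3.5² / 1.8² ≈ 60, so 180 in total against about 185. At 61 and 124 the power is 0.908 against about 90%.

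**Formulas.**
- Relative increase in variance: r = λ/(1 − λ)
- Default pooled df: ν = (m − 1)(1 + 1/r)²
- Observed-data df: ν_obs = [(EDF + 1)/(EDF + 3)] × EDF × (1 − λ)
- Barnard-Rubin df, used when EDF= is given: 1/(1/ν + 1/ν_obs)

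**Central case (EDF 60, λ = 0.10).** r = 0.111, so ν = 499 × 10² = 49,900 and the critical value is 1.960. ν_obs = (61/63) × 60 × 0.9 = 52.3, the combined df are 52.2 and the critical value is 2.006. P(t with 52.2 df > 1.960) = 0.0277. The Barnard-Rubin interval is 2.4% wider.

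| EDF | λ | Default df | Barnard-Rubin df | Critical value | Level of code as written | Interval should be wider by |
|---|---|---|---|---|---|---|
| 60 | 2% | 1,247,500 | 56.9 | 2.003 | 0.0275 | 2.2% |
| 60 | 10% | 49,900 | 52.2 | 2.006 | 0.0277 | 2.4% |
| 60 | 30% | 5,544 | 40.4 | 2.021 | 0.0284 | 3.1% |
| 50 | 10% | 49,900 | 43.3 | 2.016 | 0.0282 | 2.9% |
| 50 | 30% | 5,544 | 33.5 | 2.033 | 0.0292 | 3.7% |

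With no missing data and 60 df the level is P(t > 1.960) = 0.0273. For 185 patients (EDF 180, λ = 10%) the df are 159.7 and the level is 0.0259. The excess over 0.025 therefore goes from about 0.0009 to 0.0027.

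**Where it decides the result.** In the central case the printed one-sided p-value would have to be about 0.0224 or less to hold 0.025. Only results between about 0.022 and 0.025 change.

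**Net type I error.** The table takes Rubin's variance as correct. To test that, null trials were simulated at 43:22 with 10% dropout, sequential predictive mean matching (50 imputations per trial, df computed for m = 500) and a week-15 ANCOVA in place of the MMRM. Dropout timing and between-visit correlations of 0.6 to 0.7 were assumed.

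| Active-arm dropouts treated as MNAR | Without EDF= | With EDF= |
|---|---|---|
| none | 0.0286 | 0.0255 |
| half | 0.0250 | 0.0229 |
| all | 0.0209 | 0.0187 |

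The Monte Carlo standard error is 0.0015 to 0.0019. In each row the omission adds 0.2 to 0.3 percentage points, but the net level falls as the MNAR share rises. A second set-up, with λ at about 11 to 12%, gave lower net levels without EDF= (0.0199 at half MNAR, 0.0149 at all). The direction of the offset is therefore stable and its size is not.

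**The case against.** The strongest reply has four parts.

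First, the code agrees with the pooling text. The default PROC MIANALYZE df are the large-sample rule of Rubin (1987), which section 6.2.3 cites, and Kenward-Roger is assigned to the MMRM and used there. This stands. The mismatch is with the small-sample df planned for the model, not with the cited pooling reference.

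Second, the Kenward-Roger correction is not wholly lost, because the adjusted standard error reaches the pooling through STDERR. This also stands.

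Third, a reader might infer that the primary test exceeds 0.025 and that every pooled interval is too narrow. The SAP does not support that as a general statement. It imputes MNAR active-arm dropouts by jump-to-reference, for which Rubin's variance tends to be too large, and section 2.4 expects 10% MNAR data. In the simulated cases nearest to that expectation the code as written gave 0.0250 and 0.0209.

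Fourth, adding EDF= moves those cases further below nominal, to 0.0229 and 0.0187, in a trial already reduced in size.

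The third and fourth parts limit the claim but do not remove it. The offset comes from a different feature of the analysis and depends on a mix of dropout reasons not known in advance. Section 4.3 classes intermittent gaps, loss to follow-up and COVID-19 terminations as MAR. If those dominate, or if little is missing, the excess remains.

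**Conclusion.** The point holds in a limited form. As coded, the pooled p-value and 95% interval use large-sample df, although the plan chose Kenward-Roger df for the model. Under the stated assumptions on EDF and λ, the df omission alone raises the one-sided level from 0.025 to about 0.0275 to 0.029 and narrows the interval by about 2 to 4%. At the initial 185 patients the level would have been about 0.026.

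Whether the complete procedure is anti-conservative depends on the missing data: yes when they are few or mainly MAR, not necessarily when most active-arm dropouts are MNAR. The effect is small and changes the conclusion only for a borderline p-value, but that p-value opens or closes the whole testing hierarchy. The interim futility rule is unaffected, because section 10.4 uses the estimate and standard error without df.

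**What to change.** - In Appendices 1 and 2, keep the Kenward-Roger df from the PROC MIXED output and average them over imputations for the week-15 contrast. Give that mean to PROC MIANALYZE as EDF=.
- EDF= takes one number per call, while the code pools by visit and arm (and by shift in Appendix 2). Use separate calls per visit where the df differ.
- Apply the same rule to the key secondary endpoints, each with its own df.
- State in section 6.2.3 that pooled p-values and confidence intervals use the Barnard-Rubin df.

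This should be done before the interim analysis, because sections 2.5.1 and 10.1 bar later changes to the main analysis of the primary and key secondary endpoints. The cost is a few lines of code, slightly larger p-values, and a somewhat more conservative test if most dropouts turn out to be MNAR.
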